**Number of RBC and Whole Blood Transfusion Events**

- RBC and Whole Blood Transfusion Events are defined by grouping together on-treatment transfusion records
- Transfusion records are grouped into the same Transfusion Event if the transfusion start/end dates match with or are contained within an Admission/Discharge period, (based on the Hospitalization page in the eCRF). For example the following transfusion records would be grouped into a single Transfusion Event, because each transfusion is contained within the same hospital admission/discharge period:

Dose	Frequency	Transfusion Dates		Hospitalisation		Comment
		Start Date	End Date	Admission	Discharge	
1 unit	Once only	16FEB2019	16FEB2019	15FEB2019	26FEB2019	1 Transfusion Event
1 unit	Once only	19FEB2019	19FEB2019	15FEB2019	26FEB2019	

- Transfusion records not matching with an Admission/Discharge period are considered to be the same Transfusion Event if the gap between transfusions is 5 days or less, with further details provided below. For any subject where the frequency is PRN and the transfusion start date  $\neq$

**CONFIDENTIAL**

204837

end date, the dates of individual transfusions are unknown and the number of transfusion events will be set to missing/unknown.

- In the case of a sequence of more than two transfusions, transfusions are considered to be the same Transfusion Event if the gap between each transfusion and the first transfusion in the sequence (the “anchor” transfusion) is 5 days or less. The first transfusion that is greater than 5 days after the “anchor” transfusion is not included in the Transfusion Event, and it becomes the new “anchor” transfusion for a new Transfusion Event.
- In the example below, transfusion records 1 and 2 would be grouped into a single Transfusion Event, because the gap between the transfusions (17JAN2019 to 18JAN2019) was 5 days or less. Record 3 falls outside this Transfusion Event because the gap between the start date (22JAN2019) and the previous anchor date (16JAN2019) is more than 5 days. Therefore 22JAN2019 becomes the new “anchor” transfusion used to define the next Transfusion Event. This pattern is repeated, if necessary. N.B. “anchor” transfusions are shown in bold.

#	Dose	Frequency	Transfusion Dates		Comment
			Start Date	End Date	
1	1 unit	Once only	16JAN2019	16JAN2019	1 Transfusion Event
2	1 unit	Once only	19JAN2019	19JAN2019	
3	1 unit	Once only	22JAN2019	22JAN2019	1 Transfusion Event
4	1 unit	Once only	25JAN2019	25JAN2019	
5	1 unit	Once only	28JAN2019	28JAN2019	1 Transfusion Event

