### *RBC and Whole Blood Transfusions*

Endpoint / Variables

 
• Number (%) of participants who receive at least one RBC or whole blood transfusion by Week 52
 
• Number of RBC and whole blood transfusion events per 100 patient years
 
• Number of RBC and whole blood transfusions per 100 patient years
 
• Number of RBC and whole blood units per 100 patient years
 
• Time to first RBC and whole blood transfusion
 

Planned Exploratory Displays

 
• Summary and analysis tables will use the All Randomized (ITT) population.
 
• The total number of on-treatment RBC and whole blood transfusion events, transfusions and units for each subject will be derived as described in Section 14.6.3
 
• The number of on-treatment RBC and whole blood transfusion events per subject, the number of subjects with at least one RBC and whole blood transfusion event, and total number of RBC and whole blood transfusion events will be summarized.
 
• The number of on-treatment RBC and whole blood transfusion events per 100 patient years will be summarized by treatment group.
 
• The number of on-treatment RBC and whole blood transfusions per 100 patient years will be summarized by treatment group.
 
• The number of on-treatment RBC and whole blood units per 100 patient years will be summarized by treatment group.
 
• The reason for transfusion events will be summarized.
 
• The above summaries will be produced for the Evaluation Period and Week 52.
 
• An analysis of time to first RBC or whole blood transfusion will be performed as described in section 14.6.3, including a Kaplan-Meier plot.
 
• All transfusion summaries will be repeated for the primary definition of ESA hyporesponder subgroups (see Section 14.6.2).
 

CONFIDENTIAL

204837

*Dose Adjustment Scheme*

Endpoint / Variables

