**CONFIDENTIAL**

204837

- For records with a frequency of “PRN”, the number of transfusions for each record will be equal to the number of units recorded
- For other transfusion records, the number of transfusions will equal the duration (end date – start date +1) times a multiplier, as defined below. The number of transfusions should be rounded to nearest integer.

Frequency	Multiplier
QM	0.033
Every 2 weeks	0.071
Once a week	0.14
Q4D	0.25
2 times per week	0.29
Q3D	0.33
3 times per week	0.43
Every other day	0.5
4 times per week	0.57
5 times per week	0.71
BID	2
Q12H	2
TID	3
Q8H	3
QID	4
Q6H	4
5 times per day	5
Q4H	6

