### Number of Units

- The number of RBC and whole blood units are derived from blood transfusion records. The number of units associated with each record is determined by the frequency, start date, end date and dose (i.e. number of units recorded), as described below.
- Only units associated with on-treatment transfusions are included. “End date” below refers to the end date defined for the transfusion, or the end of the on-treatment period, if sooner (see Section [14.4.1.1](#)).
- For records with the frequency recorded as “Once only” or “Continuous infusion”, the total number of units associated with each record is the number of units recorded (regardless of start and end dates)
- For records with the frequency recorded as “Once daily”, the total number of units associated with each record will equal the number of units recorded multiplied by the duration (end date – start date +1)
- For records with the frequency recorded as “PRN”, the total number of units will be equal to the number of units recorded (regardless of start and end dates)
- For other records, the number of units will equal to the number of units recorded multiplied by the duration (end date – start date +1) times a multiplier, as defined for Number of RBC and Whole Blood Transfusions above
- The table below provides multipliers for converting various reported units to Units (which should be rounded to nearest integer). For example, a transfusion of 450ml represents a single unit:  
 $(450 \times 0.0025) = 1.125$  (rounded to 1 Unit)

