
 
Only transfusion events with a start date from the date of randomization to the date of the week 52 visit will be included
 
Patient Years (PY) = (cumulative total time from date of randomization to the date of the week 52 visit, for subjects who did not withdraw from study treatment prior to week 52 + cumulative time from date of randomization to the date of withdrawal from study treatment, for subjects who withdrew from study treatment prior to week 52) / 365.25
 
Transfusion Events per 100 PY = (100 * number of on-treatment RBC or whole blood transfusion events from the date of randomization to the date of the week 52 visit) / Patient Years (PY)
 
Transfusions per 100 PY = (100 * number of on-treatment RBC or whole blood transfusions from the date of randomization to the date of the week 52 visit) / Patient Years (PY)
 
Units per 100 PY = (100 * number of on-treatment RBC or whole blood transfusion units from the date of randomization to the date of the week 52 visit) / Patient Years (PY)
 
	
Time to First On-Treatment RBC or Whole Blood Transfusion	

 
Event Date = Start date for the first on-treatment RBC or whole blood transfusion received after treatment start date
 
Censoring Date = date of stopping study treatment for subjects who stopped study treatment, or date of study completion for subjects who did not stop study treatment
 
Time to event (days) = date of event – treatment start date +1
 
Censored time (days) = censoring date – treatment start date + 1
 
	

CONFIDENTIAL

204837

 
• Person years (PY) = (cumulative total time to event date, for subjects who received at least one on-treatment RBC or whole blood transfusion + cumulative total of censoring time for subjects who did not receive at least one on-treatment RBC or whole blood transfusion) / 365.25
 
• Incidence rate per 100 PY = (100 * number of subjects who received at least one on-treatment RBC or whole blood transfusion) / person years
 
• Absolute rate difference (per 100 person years) = daprodustat incidence rate (per 100 person years) – rhEPO incidence rate (per 100 person years)
 

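### A multi-day PRN transfusion record sets a subject's transfusion-event count to missing while patient-years are kept, so the exploratory event rate can only be too low

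*SAP*

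**What the plan says.** SAP 14.6.3.4 builds transfusion events by grouping on-treatment transfusion records. Records inside one hospital stay form one event. For the rest, "Transfusion records not matching with an Admission/Discharge period are considered to be the same Transfusion Event if the gap between transfusions" does not exceed 5 days. In longer sequences a transfusion joins the event "if the gap between each transfusion and the first transfusion in the sequence", called the anchor, is 5 days or less; the first one beyond that becomes the new anchor.

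The bullet on records outside a hospital stay also holds an exception. It opens "For any subject where the frequency is PRN and the transfusion start date" is not equal to the end date, and concludes that "the dates of individual transfusions are unknown and the number of transfusion events will be set to missing/unknown".

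The event rate is 100 times the number of events divided by patient-years. For randomization to Week 52, the denominator is "cumulative total time from date of randomization to the date of the week 52 visit, for subjects who did not withdraw from study treatment", plus time to treatment withdrawal for those who did withdraw. The Evaluation Period denominator is built the same way. Neither definition removes a subject whose event count is missing.

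Elsewhere in 14.6.3.4 the same PRN record is counted. For transfusions, "the number of transfusions for each record will be equal to the number of units recorded". Units are taken as recorded whatever the dates. Time to first transfusion uses the start date of the first on-treatment transfusion. SAP 7.4.1 also plans to show "the number of subjects with at least one RBC and whole blood transfusion event".

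**The concern.** A PRN record spanning several days leaves the dates of the individual transfusions unknown, but not whether any transfusion took place. At least one event is certain. Setting the count to missing discards that certainty while the subject's time on treatment stays in the denominator. Because the exception is worded per subject, it can also remove that subject's other events, whose dates are known.

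At stake is the internal consistency of the exploratory transfusion results. The same record contributes to transfusions, units and time to first transfusion, but not to events. The number of subjects with at least one event may then differ from the number with at least one on-treatment transfusion that accompanies the time-to-first analysis. The transfusion summaries are repeated by hyporesponder subgroup, where denominators are smaller and one lost event weighs more.

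**Working it through.** **1. The SAP's grouping example.** Five once-only records fall on 16, 19, 22, 25 and 28 January. 19 − 16 = 3 days, so the second joins the first. 22 − 16 = 6 > 5, so a new event starts. 25 − 22 = 3 joins it. 28 − 22 = 6 > 5 starts another. The result is 3 events, as the SAP shows.

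**2. What one PRN record can contain.** Let D be the duration in days (end − start + 1) and U the units. PRN transfusions equal units, so there are at most U of them. Separate events need anchors at least 6 days apart, so the number of events lies between 1 and min(U, floor((D − 1)/6) + 1).

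| Units | Days | Minimum | Maximum |
|---|---|---|---|
| 2 | 2 | 1 | 1 |
| 3 | 5 | 1 | 1 |
| 3 | 10 | 1 | 2 |
| 3 | 20 | 1 | 3 |
| 4 | 30 | 1 | 4 |

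Taken alone, a one-unit record or a record of up to 6 days is exactly one event under the SAP's own rules, yet the exception calls it unknown. For longer records only the upper count is in doubt.

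**3. Effect of one lost event.** The planned arm sizes are 134 (epoetin alfa) and 268 (daprodustat), from Protocol 10.1.1. Assume that every participant stays on treatment throughout, and take 365.25 days per year as in SAP 14.6.1.

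- To Week 52: 134 × 364/365.25 = 133.5 patient-years; 268 × 364/365.25 = 267.1. One event is 100/133.5 = 0.75 and 100/267.1 = 0.37 per 100 patient-years.
- Evaluation Period (24 weeks): 134 × 168/365.25 = 61.6; 268 × 168/365.25 = 123.3. One event is 1.62 and 0.81 per 100 patient-years.

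The absolute effect per event is twice as large on epoetin alfa because that arm is half the size. Early treatment discontinuation would shorten the denominators and raise these figures.

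**4. Illustration with assumed counts.** Suppose 27 true events on epoetin alfa to Week 52, with two affected participants who have one event each.

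- True rate: 100 × 27/133.5 = 20.2.
- As written: 100 × 25/133.5 = 18.7, which is 7.4% lower (2/27).
- Removing both participants' time as well: 100 × 25/(133.5 − 2 × 364/365.25) = 100 × 25/131.5 = 19.0, still below 20.2.

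Dropping the time does not cure the problem, because a participant is excluded only for having been transfused.

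**5. Range.** With no such records the effect is zero. With true rates of about 10 to 40 per 100 patient-years and 1 to 3 affected participants per arm, each with 1 or 2 events, the understatement runs from 1.9% (1/53) to 46% (6/13) on epoetin alfa and from 0.9% (1/107) to 22% (6/27) on daprodustat. These inputs are assumptions; the documents give none of them.

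**The case against.** The strongest reply is that little depends on this. The event measure is an exploratory summary added by the SAP (Table 1), and no between-arm test of it is planned. The protocol's three transfusion endpoints (participants with at least one transfusion, transfusions per 100 patient-years, units per 100 patient-years) can all be obtained with the record counted. Time to first transfusion, which does have a model, counts it as well. All of this stands. A reader might infer that transfused participants vanish from the transfusion results or are treated as event-free throughout; the documents do not support that.

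The exception also sits in the bullet on records not matched to a hospital stay, so a multi-day PRN record within one admission may already be a single event. That is a fair reading, although the per-subject wording leaves it open.

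The SAP says missing, not zero, and does not state how a missing count enters the rate. This is true, and the omission is part of the problem. Summing the available counts over the stated denominator gives the effect described.

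Two further inferences are tempting. One is that the rule selectively removes heavily transfused participants. Nothing in the documents links PRN entry to repeated transfusion, and Protocol 7.9 requires study treatment to stop if more than two units were needed for a reason other than acute bleeding. The other is that the between-arm comparison will shift. The rule is the same in both arms, and no difference in such records is documented. Nor is disagreement among the three rates a sign of error by itself, since events, transfusions and units differ by design.

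**Conclusion.** The point holds, within narrow limits. As written, the plan omits events that certainly occurred from the events-per-100-patient-years rate, from total events and possibly from the count of subjects with an event. Each affected subject has at least one event, so the rate to Week 52 is understated whenever such a subject exists, and no event rate can be overstated by this route. The loss of the subject's other dated events depends on reading the per-subject wording literally.

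The overall size cannot be stated; only the per-event effects are firm, and they assume planned arm sizes and full time on treatment. The correction is worth making because the SAP's own rules already settle part of what it declares unknown. It has no bearing on the trial's main conclusions.

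**What to change.** In SAP 14.6.3.4, replace the exception as follows.

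- Count each on-treatment multi-day PRN record as at least one event dated at its start date, then apply the existing hospitalization and 5-day grouping rules.
- Keep the subject's other dated events and all of the subject's patient-years, and state this denominator rule.
- As a sensitivity analysis, use the per-record upper bound min(units, floor((duration in days − 1)/6) + 1), with duration cut at the end of the on-treatment period.
- Report the number of affected subjects by arm.

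Two simpler repairs should be avoided. Removing the subject's patient-years leaves the rate too low, as shown above. Taking events equal to units as the upper bound ignores the 5-day grouping: 3 units over 5 days is one event, not three.

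The cost is a wording change and a small program change, with no new data. The drawback is that the main count becomes a minimum, which a footnote should say.

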### Number of Units

- The number of RBC and whole blood units are derived from blood transfusion records. The number of units associated with each record is determined by the frequency, start date, end date and dose (i.e. number of units recorded), as described below.
- Only units associated with on-treatment transfusions are included. “End date” below refers to the end date defined for the transfusion, or the end of the on-treatment period, if sooner (see Section [14.4.1.1](#)).
- For records with the frequency recorded as “Once only” or “Continuous infusion”, the total number of units associated with each record is the number of units recorded (regardless of start and end dates)
- For records with the frequency recorded as “Once daily”, the total number of units associated with each record will equal the number of units recorded multiplied by the duration (end date – start date +1)
- For records with the frequency recorded as “PRN”, the total number of units will be equal to the number of units recorded (regardless of start and end dates)
- For other records, the number of units will equal to the number of units recorded multiplied by the duration (end date – start date +1) times a multiplier, as defined for Number of RBC and Whole Blood Transfusions above
- The table below provides multipliers for converting various reported units to Units (which should be rounded to nearest integer). For example, a transfusion of 450ml represents a single unit:  
 $(450 \times 0.0025) = 1.125$  (rounded to 1 Unit)

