## CONFIDENTIAL

204837

Objectives	Endpoints
	
 
• Number (%) of participants with a >1 g/dL increase in Hgb within any 2-week period (assessed at Week 2 through Week 8), or with a >2 g/dL increase in Hgb within any 4-week period up to Week 52
 
• Number (%) of participants with a >1 g/dL decrease in Hgb within any 2-week period (assessed at Week 2 through Week 8), or with a >2 g/dL decrease in Hgb within any 4-week period up to Week 52
 
• N (%) of participants with a Hgb value <math>\geq 12</math> g/dL during the EP
 
• Number of times Hgb <math>\geq 12</math> g/dL during the EP
 
• % of time Hgb <math>\geq 12</math> g/dL during the EP
 

 
• To compare the effect of daprodustat administered three-times weekly to epoetin alfa on measures of iron parameters
 
	
 
• Observed and change from baseline in hepcidin, ferritin, transferrin saturation (TSAT), total iron, total iron binding capacity (TIBC) across all visits
 
• Average quarterly ferritin
 
• Average quarterly TSAT
 
• Average quarterly IV iron dose/participant
 
• N (%) of participants who met iron management criteria
 
• N (%) of participants who reduced IV iron supplementation relative to baseline [defined as total iron (mg) over 4 weeks prior to randomization] during EP [defined as average monthly IV iron dose (mg) over Weeks 28 to 52]
 

 
• To compare the effect of daprodustat administered three-times weekly to epoetin alfa on the need for red blood cell (RBC) and whole blood transfusions
 
	
 
• Number (%) of participants who receive at least one RBC or whole blood transfusion by Week 52
 
• Number of RBC and whole blood transfusions per 100 patient years
 
• Number of RBC and whole blood units per 100 patient years
 

 
• Characterize the pharmacodynamic (PD) effect of daprodustat administered three-times weekly on EPO, vascular endothelial growth factor (VEGF) and RBC
 
	
 
• Maximum observed change from baseline in EPO
 
• Maximum observed % change from baseline in VEGF
 
• Change from baseline in hematocrit, RBC count, and reticulocyte count
 

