**CONFIDENTIAL**

204837

Reported Units	Multiplier
Units	1
Milliliters (ml or CC)	0.0025
Milligram (mg)	0.0025
Milligrams/millilitres (mg/ml)	0.0025

 
Where a non-integer number of units has been entered on the eCRF, this will be rounded up to the nearest integer prior to any subsequent derivation (if necessary).
 
	
Evaluation Period (Weeks 28 to 52)	

 
Only transfusion events with a start date from date of week 28 visit to the date of the week 52 visit will be included
 
Patient Years (PY) = (cumulative total time from date of week 28 visit to the date of the week 52 visit, for subjects who did not withdraw from study treatment during the evaluation period + cumulative time from date of week 28 visit to the date of withdrawal from study treatment, for subjects who withdrew from study treatment during the evaluation period) / 365.25
 
Transfusion Events per 100 PY = (100 * number of on-treatment RBC or whole blood transfusion events during the evaluation period) / Patient Years (PY)
 
Transfusions per 100 PY = (100 * number of on-treatment RBC or whole blood transfusions during the evaluation period) / Patient Years (PY)
 
Units per 100 PY = (100 * number of on-treatment RBC or whole blood transfusion units during the evaluation period) / Patient Years (PY)
 
	
Randomization to Week 52	

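### A transfusion record of less than 200 mL contributes 0 units to the units-per-100-patient-years endpoint, although the same fraction entered in units would count as 1

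*SAP*

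**What the plan says.** SAP 14.6.3.4 (Number of Units) derives the unit count from each transfusion record's dose, frequency and dates.

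- **Doses given as a volume.** A table "provides multipliers for converting various reported units to Units (which should be rounded to nearest integer". The factor for millilitres is 0.0025, so one unit corresponds to 400 mL. The section adds a worked case: "For example, a transfusion of 450ml represents a single unit", because 450 mL converts to 1.125, which is rounded to 1.
- **Doses given in units.** The rule below the table is different: "Where a non-integer number of units has been entered on the eCRF, this will be rounded up to the nearest integer". It applies before any later derivation.
- **From dose to record.** For once-only and continuous-infusion records, "the total number of units associated with each record is the number of units recorded (regardless of start and end dates". PRN records are treated the same way. For once-daily records, "the total number of units associated with each record will equal the number of units recorded multiplied by the duration". Other frequencies also multiply by duration and by a frequency factor.

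The same section (Number of RBC and Whole Blood Transfusions) counts a once-only or continuous-infusion record as one transfusion whatever its number of units. For a PRN record it sets the number of transfusions equal to the units recorded.

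The result feeds the endpoint "Number of RBC and whole blood units per 100 patient years" (SAP 2.2; protocol Section 4). It is computed for the evaluation period and for randomization to Week 52, and SAP 7.4.1 repeats the transfusion summaries by hyporesponder status. SAP 7.4 plans no testing of exploratory endpoints unless otherwise noted.

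**The concern.** The two rules handle small amounts in opposite ways. Rounding up never turns a positive entry into zero. Rounding to the nearest integer does so for anything below half a unit, and the SAP sets no floor. A participant can then have a recorded transfusion with no units, and the count for a small transfusion depends on whether the site entered millilitres or a fraction of a unit. The affected result is the unit rate and its hyporesponder breakdown. PRN records could also affect the transfusion rate, if the units recorded are taken to mean the converted value.

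**Working it through.** **Inputs (all from SAP 14.6.3.4).** Factor 0.0025 units per mL; converted volumes rounded to the nearest integer; non-integer unit entries rounded up; no minimum per record.

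**Step 1: reproduce the SAP's example.** 450 × 0.0025 = 1.125, nearest integer 1. This agrees with the SAP. It also shows that the round-up rule is not meant for converted volumes, since rounding up would give 2.

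**Step 2: zero threshold.** Nearest-integer rounding gives 0 when mL × 0.0025 < 0.5, that is, below 0.5/0.0025 = 200 mL. At 199 mL the equivalent is 0.4975, which rounds to 0. At exactly 200 mL it is 0.5, which is 1 if halves go up and 0 if halves go to the even integer. The SAP does not say which.

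**Step 3: the same quantity by each entry route (single administration).**

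| Volume (mL) | Unit equivalent | Entered in mL (nearest) | Entered in units (rounded up) |
|---|---|---|---|
| 150 | 0.375 | 0 | 1 |
| 199 | 0.4975 | 0 | 1 |
| 300 | 0.75 | 1 | 1 |
| 450 | 1.125 | 1 | 2 |
| 590 | 1.475 | 1 | 2 |
| 600 | 1.5 | 2 | 2 |

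The routes differ below 200 mL (0 against 1) and again from 401 to 599 mL (1 against 2).

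**Step 4: which records give zero.** Once-only, continuous-infusion and PRN records take the recorded units with no later step, so below 200 mL they give 0. Three once-only records of 150 mL give 3 × 0 = 0 units, while one record of 450 mL gives 1.

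**Step 5: repeated-frequency records.** Take 150 mL once daily for 3 days. Converting and rounding first gives 0 × 3 = 0. Rounding last gives 150 × 3 × 0.0025 = 1.125, so 1. The SAP does not fix this order for converted volumes. Rounding first is the plain reading, because the later formulas start from the number of units.

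**Step 6: which rule is closer to the unrounded equivalent above 200 mL.** For 450 mL, nearest is 1/1.125 = 0.89 (11% low) and rounding up is 2/1.125 = 1.78 (78% high). For 590 mL, nearest is 1/1.475 = 0.68 (32% low) and rounding up is 2/1.475 = 1.36 (36% high).

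**The case against.** The best defence is that the two inputs are different kinds of data. A volume is converted with a nominal factor to recover a count of bags, so 1.125 is conversion noise around one bag and rounding to nearest is sensible. A fraction entered in units reports a part-used bag, and rounding up counts each bag started. The SAP's own dose examples are all of one whole unit, and the protocol's rescue algorithm (Section 7.9) also speaks of whole units. No document shows that a record of less than 200 mL, or a fractional unit entry, exists.

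Most of this stands. It can explain why 450 mL is 1 unit. It does not explain why 150 mL is 0: on the bag-counting view, a small transfusion also came from one bag.

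Three stronger readings are tempting, and the documents do not support them:

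- **Volume entries are generally miscounted by a unit, an error of 50 to 100%.** That treats the rounded-up value as the truth. Step 6 shows that nearest-integer rounding is the closer rule for both volumes examined above 200 mL. Only the zeros are a complete loss.
- **Every record under 200 mL counts as 0.** This is certain only for once-only, continuous-infusion and PRN records (Steps 4 and 5).
- **The remedy is to round everything up.** That would make 450 mL 2 units, against the SAP's own example.

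**Conclusion.** The point holds as a minor inconsistency in a derivation rule. As written, a once-only, continuous-infusion or PRN record of less than 200 mL contributes no units, whereas the same fraction entered in units contributes 1. The once-only and continuous-infusion records among these are still counted as transfusions. For repeated-frequency records the zero is the plain reading but not a certain one.

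The consequence is limited. The endpoint is exploratory and untested, the rule is the same in both arms, and neither the primary hemoglobin analysis nor the principal secondary IV iron analysis uses unit counts. Transfusion events and time to first transfusion do not use them either. The size of the effect on the rate cannot be computed, because it depends on how many records are below 200 mL or entered as fractional units, and the documents do not say.

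**What to change.** Use one rule for both entry routes in SAP 14.6.3.4. Either of these works:

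1. Sum unrounded unit equivalents per participant. This removes the zeros, the route dependence and the questions about ties and order. The 450 mL example would then read 1.125 and would need editing.
2. If integers are wanted, round to the nearest integer with a minimum of 1 unit per transfusion record. This keeps 450 mL as 1 unit and makes 150 mL and 0.375 units both 1. An entry of 1.125 units becomes 1 instead of 2. The text should also say how exact halves are rounded and whether rounding comes before or after multiplying by duration.

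Under either option, say whether the units recorded for a PRN record means the converted value when transfusions are counted. The cost is one sentence in the SAP and one line of program, with no change to data collection.
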